# 6.2. Preparation, Handling and Storage of Investigational Product

**Preparation:** No preparation is needed.

**Handling:** The occupational hazards and recommended handling procedures are provided in the Material Safety Data Sheet (MSDS). The MSDS describing the occupational hazards and recommended handling precautions will be provided to site staff if required by local laws or will otherwise be available from the sponsor upon request.

**Storage:** Tazemetostat must be stored in a secure area with access limited to the investigator and authorized site staff.

# 6.3. Dosage and Administration

Tazemetostat must be dispensed or administered only to subjects enrolled in the study and in accordance with the protocol. Standard institutional procedures for administering an oral agent via by mouth will be followed. An adequate supply will be provided with instructions on home administration.

Tazemetostat will be orally administered at the RP2D of 800 mg/dose (two 400-mg tablets) given BID. In the event that PK results are not as expected in Part 1 of the study, four 200-mg tablets may be used in Part 2 of the study (see Section 6.1). An adequate supply will be provided with instructions on home administration.

Tazemetostat will be administered BID with or without food. Each dose of study drug should be given no sooner than 8 hours from the previous or next dose. If a dose is missed by over 4 hours, it should not be made up.

**Vomiting:** If the subject vomits within 30 minutes of dosing, anti-emetics should be given and a second fresh dose of study treatment given. All doses given, missed and vomited should be recorded in the dosing diary.

#### 6.4. Procurement of IP

The initial shipment of tazemetostat to a clinical site will occur after all essential regulatory documents (including, but not limited to the receipt of the signed protocol signature page, signed Form Food and Drug Administration [FDA] 1572, curriculum vitae of principal investigator and designees, Institutional Review Board [IRB]/Ethics Committee (EC)/Central Ethics Committee [CEC] approval letter, and approved informed consent form [ICF]) are collected.

Refer to the Pharmacy Manual for directions on re-supply shipments.

## 6.5. Accountability

The investigator/designee will be responsible for taking an inventory of each shipment of tazemetostat received and comparing it with the accompanying shipment form. The investigator/designee will verify the accuracy of the information on the form, sign and date it, and acknowledge the shipment receipt according to the instructions provided.

The investigator/designee must keep accurate written records of all tazemetostat received from the sponsor. Additionally, the investigator/designee must keep accurate records of the tazemetostat dispensed to subjects enrolled in this study including the quantity of tablets, lot number, date dispensed, subject initials and identification number, dose administered, balance

forward, and the initials of the person dispensing the IP. Based on the entries in the site accountability forms, it must be possible to reconcile IP delivered with that used and returned. All IP must be accounted for and all discrepancies investigated and documented appropriately.

Tazemetostat stock may not be removed from the investigative site where originally shipped without prior knowledge and consent of the sponsor or its designee. When authorized, all applicable local, state, and national laws must be adhered to for the transfer.

At the end of the study, all unused tazemetostat will be destroyed by the investigative site or sent to a designated contractor for disposal on behalf of the sponsor, per the instructions at that time. Any IP returned to the sponsor-designated contractors must be counted and verified by site personnel and the sponsor or its designee. All certificates of delivery/receipts and/or return forms must be signed prior to shipment. The IP for return must be packed in a tamper-evident manner to ensure integrity is maintained during return. All IP returned must be in accordance with local, state, and national laws and must first be authorized by the sponsor prior to shipment.

#### 7. STUDY TREATMENT

# 7.1. Treatment Assignment

Subjects will be identified by a unique subject number that will remain consistent for the duration of the study.

### 7.2. Restrictions During Study Treatment

Subjects will abstain from ingesting Seville oranges and grapefruit or grapefruit juice and foods/beverages that contain those, for 24 hours prior to the first dose of study treatment until the last dose of study treatment. Subjects should avoid prolonged exposure to sunlight while receiving study drug. In addition, subjects should take other measures to avoid UV exposure such as wearing sun screen and sun glasses, wearing protective clothing, and avoiding tanning beds.

#### 7.3. **Dose Modification**

No modification of dose is required for the following  $\geq$  Grade 3 non-hematologic toxicities:

- Transient fatigue or asthenia lasting < 24 hours
- Transient myalgia or arthralgia lasting < 24 hours
- Nausea that resolves to < Grade 2 within seven days (with or without anti-emetics)
- Vomiting that resolves to < Grade 2 within 48 hours (with or without anti-emetics)
- Diarrhea that resolves to < Grade 2 within 48 hours

Other toxicities that, in the opinion of the investigator, are possible, probably or definitely related to study treatment, should be managed per Table 3. Toxicities that are felt by the investigator to be unrelated to tazemetostat but clinically significant should be discussed with the medical monitor. In the event of an urgent unrelated toxicity, study treatment should be interrupted as per Table 3. Dose re-escalation is not permitted.

Of note, in the event of an occurrence of a secondary neoplasm, including T-cell lymphoma, study treatment will be permanently discontinued. See Sections 4.3 and 11.5 or further discussion.

occur only after discussion with medical monitor

Dose Adjustmentb Toxicitya **During Therapy** Grade 1 Continue study treatment Maintain dose level All occurrences Grade 2 All occurrences Continue study treatment Maintain dose level **Grade 3c (Not Including Neutropenia)** 1st occurrence Restart at 600 mg BID Interrupt study treatment until 2nd occurrence resolved to Grade ≤1 or baselineb Restart at 400 mg BID (same or new toxicity) 3rd occurrence Discontinue study treatment Not applicable (same or new toxicity) Grade 3 Neutropenia (ANC:  $<1-0.5 \times 10^9/L$ ) Maintain dose level 1st occurrence Interrupt study treatment until Restart at 600 mg BID 2nd occurrence resolved to ANC  $\geq 1.0 \times 10^9/L$ 3rd occurrence Restart at 400 mg BID Discontinue study treatment 4th occurrence Not applicable Grade 4d Resumption of dosing may

**Table 3:** Dose Modifications for Treatment-Related Toxicities

ANC = absolute neutrophil count; BID = twice daily

All occurrences

Hold study treatment

### 7.4. Continuation of Treatment

In subjects that are potentially benefitting (CR, PR, or SD per modified RECIST or RECIST 1.1) from tazemetostat treatment and that have not incurred unacceptable toxicity, tazemetostat administration may be continued. Subjects will discontinue study treatment at the time of disease progression, development of an unacceptable toxicity, withdrawal of consent, or termination of the study.

a. Excluding alopecia and nausea, vomiting or diarrhea not receiving adequate treatment.

b. A delay of tazemetostat for more than 14 days due to any toxicity may require permanent discontinuation of study treatment. Study treatment may be resumed only after discussion with the medical monitor and a thorough assessment of the risk:benefit of resuming treatment.

c. Exclude Grade 3 anemia: Subjects are allowed to continue tazemetostat at their current dose level with transfusion per investigator discretion.

d. Grade 4 toxicity may require permanent discontinuation of study treatment. Study treatment may only be resumed after discussion with medical monitor and a thorough assessment risk:benefit of resuming treatment at 600 mg BID. Toxicity must resolve to Grade ≤ 1 or baseline before study treatment is restarted. Should the same Grade 4 toxicity recur at 600 mg BID, study treatment will be held until the toxicity resolves to Grade ≤1 or baseline. Study treatment will be discontinued or resumed at 400 mg BID following discussion with the medical monitor.

Study treatment may continue if the following parameters are met on Day 1 of each cycle:

- Platelet count must be  $\geq 50 \times 10^9/L$ ;
- ANC  $\ge 1.0 \times 10^9$ /L; and
- Any Grade 3 or higher toxicity must have resolved to Grade 1 or baseline.

Study treatment may be interrupted for up to 14 days. Treatment interruptions longer than 14 days need medical monitor approval to proceed.

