### 2.3.4 Anticipated Safety Profile

Based on the ongoing Phase 1 study in adults, the AEs occurring in >5% of subjects regardless of attribution were asthenia, anorexia, thrombocytopenia, nausea, constipation, diarrhea, vomiting, anemia, dry skin, dysgeusia, dyspnea, muscle spasms, abdominal pain, hypophosphatemia, anxiety, depression, hypertension, influenza, insomnia, neutropenia, night sweats, and peripheral edema. The possibly TRAEs seen in >5% of subjects included: asthenia, nausea, anemia, decreased appetite, muscle spasms, diarrhea, dry skin, dysgeusia, vomiting, and abnormal hair growth. There have been only two Grade 4 TRAEs: thrombocytopenia and neutropenia. There has been no evidence of secondary lymphomas or other secondary cancers in subjects exposed to tazemetostat to date. Additionally, there is the unknown risk of abnormal pregnancy outcomes and drug-drug interactions. Based on the preclinical toxicology of tazemetostat, the potential risks associated with treatment include GI AEs (nausea, vomiting, and diarrhea), lymphoid AEs (lymphoma in rats), liver AEs, renal AEs, bone AEs, and photosensitivity.

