# 6. INVESTIGATIONAL PRODUCT

## 6.1. Description

Tazemetostat (EPZ-6438) is an Epizyme investigational product (IP) and is defined as an Investigational Medicinal Product (IMP) under the European Union Clinical Trials Directive (EU CT Dir).

The contents of the package label will be in accordance with all applicable regulatory requirements. The expiry date will be printed on the label.

Tablets will be provided in 200 mg and 400 mg strengths. The 400-mg tablets will be used as primary treatment; however, if the median  $C_{max}$  of the 400-mg tablets in Part 1 of the study is greater than twice the median  $C_{max}$  observed with the 200-mg tablets used in the E7438-G000-101 FIH study, the 200-mg tablets will be considered for use in Part 2 of the study. The 200-mg tablets will be used when a dose reduction to 600 mg is required.

	Investigational Product	
Product name	Tazemetostat (EPZ-6438)	
Formulation description	200-mg tablet, 400-mg tablet	
Dosage form	Tablet	
Physical description	The 400-mg tablets are red, modified oval, biconvex, film-coated tablets with a length of approximately 18 mm. The 200-mg tablets are red, round, biconvex, film-coated tablets with a diameter of approximately 10 mm. Each strength is packaged in white high-density polyethylene bottle with a child resistant, tamper-evident polypropylene screw cap.	
Dose/Route/Schedule/Duration	800 mg/Oral/ BID/Continuous	

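### Table 3 footnote d names no dose reduction for a first or different Grade 4 toxicity in a subject already at 600 mg BID

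*Combined protocol and SAP*

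**What the plan says.** Subjects start at 800 mg BID, and Section 7.3 states that "Dose re-escalation is not permitted". In Table 3, a first Grade 3 event other than neutropenia restarts at 600 mg BID. The second carries the instruction "Restart at 400 mg BID (same or new toxicity", and the third ends treatment. Grade 3 neutropenia steps down one occurrence later.

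The Grade 4 row covers all occurrences. It holds treatment, allows resumption only after discussion with the medical monitor, and gives no dose. The dose is in footnote d, which:

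- opens with the possibility of stopping: "Grade 4 toxicity may require permanent discontinuation of study treatment";
- then names one dose: "Study treatment may only be resumed after discussion with medical monitor and a thorough assessment risk:benefit of resuming treatment at 600 mg BID";
- requires resolution to Grade 1 or lower, or to baseline, before any restart;
- adds one further case: "Should the same Grade 4 toxicity recur at 600 mg BID", treatment is held again, and then "Study treatment will be discontinued or resumed at 400 mg BID following discussion with the medical monitor".

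Section 6.1 treats 600 mg as a step down from the full dose: "The 200-mg tablets will be used when a dose reduction to 600 mg is required".

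**The concern.** Footnote d reads as if every Grade 4 event begins at 800 mg BID. From there, 600 mg BID is a proper reduction. But the Grade 3 rows can bring a subject to 600 mg BID with no earlier Grade 4 event, and so can an earlier Grade 4 event of another kind. In both situations the one dose the footnote puts forward is the dose at which the toxicity occurred. The re-escalation bar does not help, because going from 600 to 600 mg BID is not an escalation.

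The Grade 3 row handles the parallel situation differently. It lowers the dose at a second event whether the toxicity is the same or new, while footnote d lowers it only for the same toxicity. The documents give no reason for the difference. At stake is the safety of the few subjects who have a Grade 4 toxicity while already on a reduced dose.

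**Working it through.** **Tracing the rule by dose at onset.** Inputs are Table 3, its footnote d and the re-escalation bar in Section 7.3.

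| Event | Dose named if treatment resumes | Reduction? |
|---|---|---|
| Grade 4 at 800 mg BID | 600 mg BID | Yes |
| Same Grade 4 recurring at 600 mg BID | 400 mg BID, or discontinue | Yes |
| First Grade 4 at 600 mg BID, after a Grade 3 reduction | 600 mg BID | No |
| Different Grade 4 at 600 mg BID, after an earlier Grade 4 | 600 mg BID | No |
| Comparator: second Grade 3 non-neutropenia event at 600 mg BID, same or new | 400 mg BID | Yes |
| Grade 4 at 400 mg BID | 600 mg BID named but barred as re-escalation | No authorised restart dose |

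The shortest paths into the gap take two events:

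- Grade 3 then Grade 4: 800, 600, 600 mg BID.
- Two different Grade 4 toxicities: 800, 600, 600 mg BID.

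Two Grade 3 non-neutropenia events give 800, 600, 400 mg BID. Reaching Grade 4 at 400 mg BID takes at least three events.

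**How many subjects.** The plan gives no figure for this, so what follows is a rough estimate from Phase 1.

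- Section 2.3.4: "There have been only two Grade 4 TRAEs: thrombocytopenia and neutropenia".
- Section 2.2.5: four treatment-related events of Grade 3 or higher among 58 subjects. One Grade 4 event was at 1600 mg BID, twice the dose used here.
- Planned enrolment: 67.

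Assume that both Grade 4 events fall among the 58 and in different subjects, and that the four events include these two, leaving two Grade 3 events, also in different subjects.

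- Grade 4 rate: 2/58 = 3.4% (exact 95% CI 0.4% to 11.9%).
- Expected subjects with any Grade 4 event: 67 × 2/58 = 2.3.
- Expected subjects with both a Grade 3 and a Grade 4 event, under independence: 67 × (2/58) × (2/58) = 0.08.
- If an earlier Grade 3 event raises the Grade 4 risk fivefold (assumed): 5 × 0.08 = 0.4.
- Stress case, both rates at the upper limit: 67 × 0.119 × 0.119 = 0.95.

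The product ignores the order of events, and Table 3 exempts some Grade 3 events such as anemia. Both make 0.08 generous for this path. For the path with two different Grade 4 toxicities, if a second is taken to be as likely as a first, the same product gives at most another 0.08.

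**The case against.** The strongest reply is that the Grade 4 pathway as a whole is the more guarded one. After a second Grade 3 event, treatment restarts on resolution, with no medical monitor step unless the delay exceeds 14 days. After Grade 4 toxicity every restart is optional and needs resolution, monitor discussion and a thorough risk:benefit assessment, and permanent discontinuation is available. Section 7.4 also stops treatment for unacceptable toxicity, and the data monitoring committee reviews safety. This stands. A reader might infer that the protocol orders re-dosing at 600 mg BID, or that it protects Grade 4 subjects less overall. The text supports neither. What remains is narrower: the only dose named for that discussion is the one at which the event occurred.

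A reader might also infer that a subject with Grade 4 toxicity at 400 mg BID could be sent back up to 600 mg BID, or is left without any rule. That does not follow. The re-escalation bar rules out 600 mg BID, and the hold, resolution, monitor and discontinuation provisions still apply.

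The last sentence of footnote d could be read alone as allowing 400 mg BID after any Grade 4 event. It directly follows the sentence on recurrence of the same toxicity and completes that case, so the general reading is strained.

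Finally, the Grade 3-then-Grade 4 path assumes that the Grade 4 event is not counted as a second occurrence in the Grade 3 row. The documents do not say whether counts are shared. If they are, that path could lead to 400 mg BID. Grade 4 has its own row and footnote, so separate handling is the more natural reading, but this is a real dependency.

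**Conclusion.** The point holds as a narrow gap in a stated safety rule. For a first or different Grade 4 toxicity at 600 mg BID, footnote d names no reduction, while a second Grade 3 non-neutropenia event at that dose brings one. Onset at 400 mg BID needs no more than a clarification.

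The expected number affected is well under one, about 0.08 of 67 subjects on the main route under independence. The 0.4 figure rests on an assumed multiplier and 0.95 is a stress case. The 2/58 rate is itself insecure: Section 2.2.5 places the neutropenia event in an expansion cohort, whereas Section 2.4.2 describes the 58 as dose-escalation subjects. No effect on the Week 12 disease control rate or the Part 2 design follows from any of this. The change is worth making because the individual consequence is serious and the cost is a few words.

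**What to change.** Amend footnote d in two places:

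- Any resumption after Grade 4 toxicity is one dose level below the dose at onset: 800 to 600 mg BID, 600 to 400 mg BID.
- The choice between discontinuing and resuming at 400 mg BID applies to any Grade 4 toxicity at 600 mg BID, whether the same as before or new.

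The requirements for resolution, monitor discussion and risk:benefit assessment stay as they are. As minor clarifications, state discontinuation for Grade 4 toxicity at 400 mg BID, and say whether occurrence counts are shared between the Grade 3 and Grade 4 rows. A separate sentence against restarting above the dose at onset would largely repeat Section 7.3 and is not needed.

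The cost is a wording change in a protocol amendment, with no added procedures, subjects or changes to the statistical analysis.

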# 7.5. Treatment Compliance

The subject will be requested to maintain a medication diary of each dose of tazemetostat. The dosing diary will be returned to the site staff at each visit.

#### 7.6. Treatment of Overdose

In the event of an overdose of tazemetostat (defined as administration of more than the protocol-specified dose), the investigator should contact the medical monitor or their designee immediately and closely monitor the subject for AEs/SAEs and laboratory abnormalities.

A subject suspected of overdose should be monitored until tazemetostat can no longer be detected systemically. For reference, five half-lives of tazemetostat would be at minimum 25 hours, longer in subject with delayed clearance. Decisions regarding dose interruptions or modifications will be made by the investigator in consultation with the medical monitor or their designee based on the subject's clinical evaluation.

A plasma sample for PK analysis may be requested on a case-by-case basis. If requested, the plasma sample should be collected at least within 7 days from the date of the last dose of study treatment.

The quantity of the excess dose as well as the duration of the overdosing should be documented in the electronic case report form (eCRF).

#### 7.7. Tazemetostat Duration of Treatment

Treatment with tazemetostat will continue until disease progression or unacceptable toxicity.

Subjects may receive tazemetostat for an approximate duration of 12 months. (Note: If treatment is discontinued prior to completing 12 months, subjects will be followed for a maximum duration of 12 months from start of study drug dosing). Those subjects who continue to derive clinical benefit from tazemetostat after 12 months of treatment may continue treatment on the current study as long as it is open and actively treating subjects. Once all subjects have

had the opportunity to receive 12 months of treatment, the active portion of the study may be closed per sponsor decision. Any subjects continuing to receive clinical benefit may rollover and continue to receive treatment on an extension study at the discretion of the investigator after discussion with the medical monitor.

#### 8. STUDY ASSESSMENTS AND PROCEDURES

Investigators may be requested to perform additional safety tests during the course of the study based on newly available data to ensure appropriate safety monitoring. Appropriate local regulatory and ethical approvals should be obtained before any additional testing is performed.

#### 8.1. Consent

All subjects must take part in the informed consent process. Adequate time must be allowed for the subject to ask questions and make a voluntary decision. No protocol-specific procedures, including screening procedures are to be performed until the subject has signed and dated an IRB/IEC/CEC-approved ICF.

# 8.2. Screening Assessments

A signed, written informed consent must be obtained prior to any study-specific assessments or procedures being performed.

All screening assessments, including tumor assessment, must be performed within 21 days of enrollment.

Procedures conducted as part of the subject's routine clinical management (e.g., blood counts, chemistries, imaging studies) and obtained prior to consent may be used for screening provided the procedure meets the protocol-defined criteria and has been performed in the timeframe of the study.

#### 8.2.1 Demographics and Medical History

A complete medical history will be taken. Information to be documented includes demographic information, prior medical illnesses and conditions, and surgical procedures.

# 8.3. Study Assessments

For study assessments not included in sections below (e.g., vital signs, ECOG performance status), refer to the Schedule of Assessments (Table 1) for details.

#### **8.3.1** Physical Examinations

#### 8.3.1.1. Comprehensive Physical Examination

A comprehensive physical examination (PE) of all body systems must be performed by a qualified licensed individual at screening, on Day 1 of each cycle through Cycle 8, and starting on Day 1 of Cycle 9, once every 6 weeks. In addition, a complete PE is to be performed at the Post-Treatment/Early Termination visit. A review of body systems will include the following:

• General appearance

- Skin
- Head, Ears, Eyes, Nose, Throat (HEENT)
- Respiratory
- Cardiovascular
- Abdomen (including liver and kidneys)
- Musculoskeletal

Weight is required to be measured on Day 1 of each cycle. Height measurement is required at screening only.

Any abnormalities or changes in intensity noted during the review of body systems should be documented in the source document and reported appropriately in the eCRF. If a new clinically significant finding (e.g., not noted at screening) occurs from the initial tazemetostat administration until the end of the study, an AE must be documented. In addition, resolution of any abnormal findings during the study will be noted in source document and the eCRF if clinically significant.

These assessments will be completed as indicated in the Schedule of Assessments (Table 1).

